Pain is typically categorized as mild or moderate. Flexible cystoscopy, often performed in outpatient settings, is one measure aimed at alleviating procedural discomfort. However, despite the use of these advanced instruments, patient-reported discomfort remains similar to traditional methods. Notable gender differences suggest that males experience greater pain compared to females. The most painful stage is during cystoscope insertion, particularly when passing through the external urethral sphincter.

We conducted a study to evaluate the comparative efficacy of lidocaine gel and lidocaine injection in irrigation during outpatient rigid cystoscopy examination.

2. Research Programs and Plans

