2.2 Arms and interventions

Arms	Assigned Interventions

Sham Comparator:
 
Intraurethral lidocaine gel alone
 
Participants received 10 ml of intraurethral lidocaine gel at a concentration of 2%
	
Drug: Intraurethral lidocaine gel alone
 
participants received 10 ml of intraurethral lidocaine gel at a concentration of 2%
 
Other Names: Group A

Experimental:
 
Intraurethral lidocaine gel + lidocaine 2% injection
 
Participants received 10 ml of intraurethral lidocaine gel at a concentration of 2% and using the injection of lidocaine 2% to irrigate the urethra using a 20ml syringe.
	
Drug: Intraurethral lidocaine gel + lidocaine 2% injection
 
participants received 10 ml of intraurethral lidocaine gel at a concentration of 2% and using the injection of lidocaine 2% to irrigate the urethra using a 20 ml syringe.
 
Other Names: Group B

Experimental:
 
intraurethral lidocaine gel +
	
Drug: intraurethral lidocaine gel + liquid paraffinl

liquid paraffin
 
Liquid paraffin were used to lubricate the cystoscopy tube AND
 
Lubricate the cystoscopy tube AND participants received 10 ml of
 
10 ml of intraurethral lidocaine gel at a
 
lidocaine gel
 
at a concentration of 2%
	
Liquid paraffin were used to lubricate the cystoscopy tube AND
 
participants received 10 ml of intraurethral lidocaine gel at a concentration of 2%
 
Other Names:
 
Group C

--	---

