2.3 Outcome Measures

2.3.1 Primary Outcome Measure:

Access the pain score using the Visual Analogue Scale (VAS) during the procedure. Time Frame: The procedure was evaluated using the visual analogue scale immediately afterward (referred to as "during the procedure" for the study's purposes) and again five minutes later.

2.3.2 Secondary Outcome Measures:

Postoperative complications including included parameters such as field of view occlusion, duration of pain, hematuria duration, and lower urinary tract symptoms post-procedure. Time Frame: Within three days after surgery.

3. Data management and quality control

The investigator loads data into the case report form in a timely, complete, correct, and legible manner based on the subject's original observation record. The questionnaire after review and signature by the ombudsman should be sent to the clinical research data manager in a timely manner.

The entry is done using the appropriate database system of two-person dual-machine entry, after which the database is compared twice, during which the monitor is notified promptly if any problems are found, and the researcher is asked to make a reply. The exchange of questions and answers between them should be in the form of a questionnaire, which should be kept for reference.

Statistical Analysis Plan

After data collection, descriptive and analytical analyses were conducted using SPSS version 26. Between-group differences were assessed using independent samples analysis of variance (ANOVA). Due to the significant result of the Shapiro-Wilk test, non-parametric tests (Kruskal-Wallis test) were employed for statistical analysis. Dwass-Steel-Critchlow-Fligner test was used as a post-hoc analysis to delineate specific between-group differences in mean pain scores and other surgery-related data. Data are presented as mean (M) \pm standard deviation (SD).

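### The objective, as literally worded, compares lidocaine gel with lidocaine irrigation, but every arm receives the same gel; the arms answer add-on questions, and the objective should say so

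*Combined protocol and SAP*

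**What the plan says.** The closing sentence of the background, just before section 2, gives the purpose of the study: to "evaluate the comparative efficacy of lidocaine gel and lidocaine injection in irrigation during outpatient rigid cystoscopy examination".

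Section 2.2 defines three arms:

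- Group A, the comparator: "Intraurethral lidocaine gel alone", 10 ml at 2%.
- Group B: "10 ml of intraurethral lidocaine gel at a concentration of 2% and using the injection of lidocaine 2% to irrigate the urethra".
- Group C: "Liquid paraffin were used to lubricate the cystoscopy tube AND" the same 10 ml of 2% gel.

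Section 2.3.1 names VAS pain as the primary outcome. On timing it says "The procedure was evaluated using the visual analogue scale immediately afterward", treats that reading as the score for the procedure itself, and then adds "and again five minutes later".

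The Statistical Analysis Plan uses a Kruskal-Wallis test, with Dwass-Steel-Critchlow-Fligner (DSCF) comparisons of all pairs of groups afterwards. It does not say which pair answers the objective or which VAS time decides the primary result. It states no significance level.

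**The concern.** The objective sets two things against each other, gel and irrigation. The arms do not: gel is given to everyone, and what differs is what is added to it. A lower score in B than in A would show that adding irrigation to gel helps. Reported under the present objective, it could be taken to mean that injected lidocaine works better than gel, which these data could neither support nor refute. The objective also leaves out paraffin, although C is one of the two experimental arms.

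A separate matter is the primary outcome. Two readings share primary status with no rule for choosing between them. DSCF adjusts across the three pairs at one time, not across the two times. A pair that is significant at only one time could therefore be presented as the primary result.

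**Working it through.** **1. Which contrasts the arms can estimate.** The plan gives no figure to reproduce here. The inputs are the arm definitions in section 2.2. Write the mean VAS score as background μ plus effects of gel (g), irrigation (i) and paraffin (p):

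- A = μ + g, row (1, 1, 0, 0)
- B = μ + g + i, row (1, 1, 1, 0)
- C = μ + g + p, row (1, 1, 0, 1)

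These rows have rank 3, for 4 parameters. A contrast can be estimated only if appending it leaves the rank at 3.

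| Contrast | Row appended | Rank | Estimable |
|---|---|---|---|
| Gel minus irrigation | (0, 1, −1, 0) | 4 | No |
| Gel against no gel | (0, 1, 0, 0) | 4 | No |
| B−A | (0, 0, 1, 0) | 3 | Yes |
| C−A | (0, 0, 0, 1) | 3 | Yes |
| B−C | (0, 0, 1, −1) | 3 | Yes |

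Only two of the last three are independent, since B−C = (B−A) − (C−A).

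An illustration with invented scores: let i = −1, p = −0.5 and μ = 5 − g. Then for any g the arm means are A = 5.0, B = 4.0 and C = 4.5.

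| g | g − i | B−A | C−A | B−C |
|---|---|---|---|---|
| 0 | +1 | −1.0 | −0.5 | −0.5 |
| −1 | 0 | −1.0 | −0.5 | −0.5 |
| −3 | −2 | −1.0 | −0.5 | −0.5 |

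The same data fit a gel-minus-irrigation difference of either sign, while the add-on contrasts do not move.

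**2. What B−A contains.** Split i into flushing and lidocaine. The three arms still have rank 3. Appending either part alone gives 4; appending their sum gives 3. B−A is therefore the effect of the whole irrigation step. It is not a comparison of routes at equal dose, and no dose multiple can be worked out because the irrigation volume is not stated.

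**3. Two VAS times (a separate issue).** Assumptions: 5% level, no true differences, equal arms, normal approximation, and correlation between the two scores of 0.5 to 0.9. None of these is given in the documents. The DSCF cut-off is the studentized range q(0.95; 3, ∞) = 3.314, and the Kruskal-Wallis cut-off is 5.991. Ungated means that pairs are read regardless of the overall test; gated means only after it is significant. Chance of at least one false pair, from 2,000,000 simulated draws:

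| Rule | Ungated | Gated |
|---|---|---|
| One named time | 5.0% | 4.5% |
| Either time, correlation 0.5 | 9.2% | 8.2% |
| Either time, correlation 0.7 | 8.5% | 7.6% |
| Either time, correlation 0.9 | 7.2% | 6.4% |

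As a plausibility bound, independent times would give 1 − 0.95² = 9.75% ungated and 1 − 0.955² = 8.8% gated. The simulated values lie below these, as they should. A check with actual tied-rank tests on whole-number 0–10 scores, at an assumed 20 or 50 per arm (40,000 draws each), gave 7.2% to 8.8% ungated and 6.2% to 7.8% gated.

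**The case against.** The strongest reply is that the objective is shorthand. Read beside the arm labels in section 2.2, gel and injection can mean gel alone and gel plus injection. That is B−A, which the trial can estimate. This is a fair reading, and it limits the point to the literal wording. It does not remove the point, because the sentence nowhere says that irrigation is added to gel.

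Several stronger conclusions might be inferred, and the documents do not support them:

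- *That the design is faulty.* It is not. The three arms form a coherent add-on design, and the fault lies in the sentence describing the question. Nor do the documents contain a conclusion that gel and injection were compared directly; the harm is a risk of misstatement.
- *That the paraffin arm has no rationale.* The opening of the document was removed before review, and a rationale could stand there. All that can be said is that the supplied text states none.
- *That the error rates measure the harm of the objective's wording.* They concern only the two VAS times. They also depend on a rule that either time may count, which section 2.3.1 does not state. That section already leans towards the immediate score by equating it with pain at the procedure. What remains is that the five-minute score sits in the same primary time frame.
- *That calling B−C secondary would tighten error control.* It would not while all three pairs stay inside one DSCF adjustment.

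**Conclusion.** The point holds in limited form. As literally worded, the objective cannot be answered at any sample size; read as an add-on question, it is answered by B−A and should be stated as such. This follows from section 2.2 alone and needs no assumption about sample size or level. A causal reading of B−A or C−A also depends on how participants were allocated, which the supplied text does not describe.

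The two-time primary outcome is a separate and smaller point. If either time could be claimed, the chance of any false pair would be about 7% to 9% ungated or 6% to 8% gated, against 5.0% or 4.5% at one named time. This rests on an assumed 5% level and an assumed correlation of 0.5 to 0.9.

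Both should be corrected. Neither invalidates the arms, the data or the planned tests.

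**What to change.** - **Objective.** Restate it as the added effect on VAS pain of lidocaine irrigation (B−A) and of liquid paraffin lubrication (C−A) over 2% lidocaine gel alone. Describe B−A as the effect of the whole irrigation add-on, and draw no conclusion about gel against injection.
- **Section 2.3.1.** Name the immediate VAS score as primary and the five-minute score as secondary.
- **Statistical Analysis Plan.** Keep Kruskal-Wallis and DSCF. Add a line saying that all three pairs, B−C included, stay in the one DSCF adjustment, and that B−A and C−A at the immediate time answer the objective.

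No arm, data item or test changes. The costs are a narrower objective and the loss of primary status for the five-minute score. There is also a cost in timing. The plan is written in the past tense ("After data collection, descriptive and analytical analyses were conducted using SPSS version 26") and reports a finding from data: "Due to the significant result of the Shapiro-Wilk test, non-parametric tests (Kruskal-Wallis test) were employed for statistical analysis". If outcome data had been seen when these choices are made, they must be labelled post hoc. They would then still govern what may be concluded, but would not carry the weight of prespecification.

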2.1 Subject of study

Subject of study: Male patients under 50 years of age with diagnosed with bladder tumors requiring postoperative cystoscopy attending the Department of Urology at the Second Xiangya Hospital from January 2024 to present.

The inclusion criteria were: 1. patients with bladder tumors need to undergo cystoscopy after surgery; 2. male patients, aged 18-50 years old, meeting the ethical criteria, and all subjects participated voluntarily and signed the informed consent form at the same time; 3. no adjuvant treatments, such as radiotherapy, chemotherapy, etc., prior to the surgery; 4. complete medical history data.

Exclusion criteria: 1. Other evident causes contributing to lower urinary tract symptoms, such as obvious glandular cystitis and severe urinary tract infections. 2. Excessive prostatic hyperplasia. 3. Urethral stricture. 4. A history of prior urethral surgeries. 5. Uncontrolled hypertension, cardiac conditions, and chronic obstructive pulmonary disease.

2.2 Arms and interventions

Arms	Assigned Interventions

Sham Comparator:
 
Intraurethral lidocaine gel alone
 
Participants received 10 ml of intraurethral lidocaine gel at a concentration of 2%
	
Drug: Intraurethral lidocaine gel alone
 
participants received 10 ml of intraurethral lidocaine gel at a concentration of 2%
 
Other Names: Group A

Experimental:
 
Intraurethral lidocaine gel + lidocaine 2% injection
 
Participants received 10 ml of intraurethral lidocaine gel at a concentration of 2% and using the injection of lidocaine 2% to irrigate the urethra using a 20ml syringe.
	
Drug: Intraurethral lidocaine gel + lidocaine 2% injection
 
participants received 10 ml of intraurethral lidocaine gel at a concentration of 2% and using the injection of lidocaine 2% to irrigate the urethra using a 20 ml syringe.
 
Other Names: Group B

Experimental:
 
intraurethral lidocaine gel +
	
Drug: intraurethral lidocaine gel + liquid paraffinl

liquid paraffin
 
Liquid paraffin were used to lubricate the cystoscopy tube AND
 
Lubricate the cystoscopy tube AND participants received 10 ml of
 
10 ml of intraurethral lidocaine gel at a
 
lidocaine gel
 
at a concentration of 2%
	
Liquid paraffin were used to lubricate the cystoscopy tube AND
 
participants received 10 ml of intraurethral lidocaine gel at a concentration of 2%
 
Other Names:
 
Group C

--	---

2.3 Outcome Measures

2.3.1 Primary Outcome Measure:

Access the pain score using the Visual Analogue Scale (VAS) during the procedure. Time Frame: The procedure was evaluated using the visual analogue scale immediately afterward (referred to as "during the procedure" for the study's purposes) and again five minutes later.

2.3.2 Secondary Outcome Measures:

Postoperative complications including included parameters such as field of view occlusion, duration of pain, hematuria duration, and lower urinary tract symptoms post-procedure. Time Frame: Within three days after surgery.

3. Data management and quality control

The investigator loads data into the case report form in a timely, complete, correct, and legible manner based on the subject's original observation record. The questionnaire after review and signature by the ombudsman should be sent to the clinical research data manager in a timely manner.

The entry is done using the appropriate database system of two-person dual-machine entry, after which the database is compared twice, during which the monitor is notified promptly if any problems are found, and the researcher is asked to make a reply. The exchange of questions and answers between them should be in the form of a questionnaire, which should be kept for reference.

Statistical Analysis Plan

After data collection, descriptive and analytical analyses were conducted using SPSS version 26. Between-group differences were assessed using independent samples analysis of variance (ANOVA). Due to the significant result of the Shapiro-Wilk test, non-parametric tests (Kruskal-Wallis test) were employed for statistical analysis. Dwass-Steel-Critchlow-Fligner test was used as a post-hoc analysis to delineate specific between-group differences in mean pain scores and other surgery-related data. Data are presented as mean (M) \pm standard deviation (SD).

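### Hematuria and urinary symptoms after cystoscopy are labelled complications, but the plan has no record of whether they were present before it (minor, secondary outcomes only)

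*Combined protocol and SAP*

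**What the plan says.** Section 2.1 enrols "patients with bladder tumors need to undergo cystoscopy after surgery", and its opening sentence describes the population as having "bladder tumors requiring postoperative cystoscopy". Every participant has therefore had a tumour operation before the study examination. No minimum interval since that operation is given.

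Section 2.3.2 introduces the secondary outcomes as "Postoperative complications including included parameters such as field of view occlusion". It goes on to duration of pain and then "hematuria duration, and lower urinary tract symptoms post-procedure". The window is "Time Frame: Within three days after surgery". No time point before the cystoscopy is mentioned.

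The Statistical Analysis Plan compares groups by ANOVA or, because normality was rejected, by the Kruskal-Wallis test with Dwass-Steel-Critchlow-Fligner post-hoc comparisons. It reports means and standard deviations. It names no baseline covariate and no change score.

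Three entry rules in section 2.1 bear on prior symptoms. Men with "Other evident causes contributing to lower urinary tract symptoms" are excluded, and so are men with "A history of prior urethral surgeries". One inclusion criterion requires "complete medical history data".

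**The concern.** Calling a symptom a complication attributes it to the procedure. A symptom already present before the study treatment cannot have been caused by it. In this population a competing source is built in: every man has been operated on for a bladder tumour, and the plan does not separate what he brought to the examination from what followed it.

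The terms do not help an assessor. In section 2.1 'postoperative' refers to the tumour operation. In section 2.3.2 'postoperative' and 'surgery' most likely refer to the cystoscopy, but the text does not say so.

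If persisting symptoms are counted, two things follow even when the arms are balanced. The complication figures are too high in every arm, and any real difference between arms is diluted, because some men contribute values that the treatment could not change.

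**Working it through.** The documents give no symptom rate, no interval since the operation and no figure for these outcomes, so there is no stated number to reproduce. All inputs below are assumptions, shown as ranges.

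**Notation.** p = share of men with persisting prior symptoms, the same in every arm; d = days of prior bleeding inside the three-day window; m = mean days of new bleeding; r = risk of new symptoms.

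**1. Dilution on the scale of the planned rank tests.** The effect is e = P(A > B) + 0.5 P(tie) - 0.5, where A and B are hematuria durations in two arms.

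Upper bound: prior bleeding fills all three days and new bleeding is always shorter.
- Two men without prior bleeding form a share (1-p)² of pairs and contribute e.
- Pairs with one prior case contribute +0.5 and -0.5 equally often and cancel.
- Pairs with two prior cases are ties and contribute 0.

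So e is multiplied by (1-p)²:
- p = 0.02: 0.98² = 0.960, a loss of 4%
- p = 0.05: 0.95² = 0.903, a loss of 10%
- p = 0.10: 0.90² = 0.810, a loss of 19%

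For shorter prior bleeding a model is needed. Take new bleeding as exponential with means 1.0 and 0.6 day, recorded in half-day steps and capped at 2.5 days, with each prior case taking the longer of new bleeding and d. The answer depends on whether durations are rounded down, to nearest or up, so the range over the three rules is given.

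| p | d = 1 day | d = 2 days | d = 3 days |
|---|---|---|---|
| 2% | 0-1% | 2-3% | 4% |
| 5% | 1-3% | 5-6% | 10% |
| 10% | 2-5% | 9-12% | 19% |

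Entries are the percentage by which the rank effect shrinks.

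**2. Inflation of the reported figures.** For mean hematuria duration, with prior bleeding lasting all three days, the mean is too high by p(3 - m):
- m = 0.5: 0.02 × 2.5 = 0.05 day; 0.05 × 2.5 = 0.125 day; 0.10 × 2.5 = 0.25 day
- m = 1.0: 0.02 × 2.0 = 0.04 day; 0.05 × 2.0 = 0.10 day; 0.10 × 2.0 = 0.20 day

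If urinary symptoms are reported as yes or no, which the plan does not say, the percentage is too high by p(1 - r). With r from 0.2 to 0.4 this is 1.6 to 1.2 points at p = 2%, 4 to 3 points at 5%, and 8 to 6 points at 10%.

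**3. What the entry rules cover.**
- The first exclusion depends on what 'other' means. If it means other than the cystoscopy, evident urinary symptoms left by the tumour operation are already excluded. If it means other than the bladder tumour and its treatment, they are not. The examples given, glandular cystitis and severe infection, do not settle it. On either reading hematuria is not named.
- The medical history criterion may hold symptom information, but it is not defined as a baseline measure and no analysis uses it.
- The source record mentioned in section 3 says where data come from, not which symptoms are noted or when.

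**The case against.** The strongest reply is that an ordinary reader takes a post-procedure complication to mean something arising from the cystoscopy, so a sensible investigator would leave out unchanged prior symptoms. The men are aged 18 to 50, the examination is outpatient, and several causes of urinary symptoms are excluded. Residual symptoms may be rare or absent. This stands as a limit on the likely size. It does not close the gap: no rule tells assessors to discount prior symptoms, and nothing in the entry rules mentions hematuria.

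A reader might infer that the comparison between arms is biased. The documents do not support that. If allocation is random, an imbalance in prior symptoms arises only by chance and the test's error rate covers it. A false difference would be a bias concern only under non-random allocation, and the visible text does not state how allocation was done. Even then the size depends heavily on the assumptions. With no true effect and prior bleeding of d days in place of new bleeding, a 5-point imbalance shifts mean duration by 0.05 × (d - m). For d from 1 to 3 days that is 0.025 to 0.125 day at m = 0.5, and 0 to 0.10 day at m = 1.0.

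It is also fair to say that the full remedy may come too late. Recruitment is dated from January 2024, and the analysis plan is in the past tense and already cites a test result. That limits what can be done for earlier patients, but the labelling of the outcome can still be corrected.

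**Conclusion.** The point holds as a minor one. As written, a post-only comparison would count persisting hematuria and urinary symptoms as complications, and the visible plan contains nothing that would separate them.

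The size is unknown and could be nil. Under an assumed 2-10% of men with prior hematuria, the rank effect shrinks by about 0-5% if prior bleeding lasts one day and by 4-19% if it lasts all three days, which is the upper bound. The one-day figure rests on an assumed distribution and rounding rule. The three-day figure needs only that new bleeding be shorter than the full window.

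Two stronger readings should be resisted. The documents do not show that any participant had residual symptoms, so it cannot be said that the complication figures are wrong, only that the plan would not detect it if they were. Nor does the problem reach the main result: the primary pain score is not affected.

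**What to change.** **Men still to be examined.** Record hematuria (yes/no) and lower urinary tract symptoms just before the cystoscopy. In section 2.3.2, define these two outcomes as new or worse than that record. In the Statistical Analysis Plan, compare the arms on that definition or adjust for baseline status. One simple option is to run the planned Kruskal-Wallis and post-hoc tests for hematuria duration in men without hematuria beforehand and to tabulate the others by arm.

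**Men already examined.** Take prior status from the medical history where it is available. Otherwise report these outcomes as 'symptoms present after cystoscopy' rather than as complications.

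**Wording.** State in the section 2.3.2 time frame whether 'surgery' means the cystoscopy.

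**Cost.** One short case report form item, one sentence in section 2.3.2 and one in the analysis plan, with no extra visit. Baseline data will be incomplete for earlier patients, and restricting the hematuria comparison to men without prior hematuria makes that group slightly smaller. Relabelling needs no new data, so it remains possible even if enrolment is complete.
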